6.14 ANALYSIS OF SECONDARY ENDPOINTS

Table 12. Generic Estimand-to-Analysis table for all secondary Day-28 immunological endpoints (specified in Table 7).

in Table 7).							
Objectives (as per Protocol):							
Binding antibody endpoints: As per Table 10							
Neutralising antibody endpoints: Compare the immunogenicity, both humoral and cellular, over 12 months following							
fractional and standard booster doses of the vaccines listed.							
Estimand:	[MoA]* of [OUTCOME]* 28 days after boosting with a single fractional dose compared to a single standard dose of either of the COVID-19 trial vaccines in adults 18 years or older in [Indonesia/Mongolia] who have been primed through previous vaccination with either of the included primary series, irrespective of SARS-CoV-2 infection.						
ESTIMAND Attributes:	Incorporation of Estimand Attribute in ANALYSIS:						
Treatment	Study arms						
As per Table 10	As per Table 10						
Target population	Analysis set ("Secondary Day-28 Immunology Population")						
As per Table 10	All randomised participants as per randomisation with complete						
	outcome and covariate data						
Variable	Outcome measure						
[OUTCOME]*, 28 days after boosting.	[OUTCOME]* at the Day-28 visit (28 – 35 days post-booster).						
Handling of intercurrent events	Handling of missing data						
As per Table 10	As per Table 10						
Population-level summary measure	Analysis approach						
Geometric mean ratio (GMR) OR Difference in	Linear regression will be used to estimate the difference in						
Means*	mean [OUTCOME]* between fractional and standard dose						
	arms, adjusted for stratifying variables (age group and primary						
	series), duration between 1st and 2nd, and 2nd and 3rd doses,						
	study day of blood-draw, and baseline [OUTCOME]* levels.						
	Where the population-level summary measure is the GMR, the						
	outcome variable (and the baseline value) will be loge						
	transformed prior to regression, and the GMR (95% CI) will be						
	calculated as the antilogarithms of the mean difference (β_1) and						
	it's 95% CI.						

^{*}This table is generic for all secondary Month-6 and Month-12 immunological endpoints (see Table 7), which will be analysed in the same way depending on their distributions; the population measure for outcomes with skewed distributions is the geometric mean and the population-level summary measure of association (MoA) is the GMR — baseline and Month-[6/12] values will be loge transformed prior to analysis; the population measure for normally distributed outcomes (ACE2 binding inhibition) is the mean and the population-level summary measure of association (MoA) is the Difference in Means.

6.15 SUPPLEMENTARY AND SENSITIVITY ANALYSES

The following supplementary and sensitivity analyses will be conducted. The supplementary analyses use alternative strategies for handling intercurrent events and thus target different estimands; the results will help to fully understand the impact of the intercurrent events and the strategies used to handle them. The sensitivity analyses target the same estimands and test the sensitivity of deviations from assumptions about missing data.⁴

Table 14. Supplementary and Sensitivity Analyses

	MAIN ANALYSIS (Complete Case)		SUPPLEMENTARY ANALYSIS (for IcE Strategy)			SENSITIVITY
			Change to Estimand			ANALYSIS (for
Endpoints	Estimand	IcE & Strategy	from Main Analysis	IcE & Strategy	Impact	>5% missingness)
Primary immunological endpoint (seroresponse at Day-28)	The difference in seroresponse proportions 28 days after boosting with a single fractional dose compared to a single standard dose of either of the COVID-19 trial vaccines in adults 18 years or older in [Indonesia/Mongolia] who have been primed through previous vaccination with either of the included primary series, irrespective of SARS-CoV-2 infection.	SARS-CoV-2 infection: Treatment Policy	, irrespective of SARS-CoV-2 infection ≤ 14 days post-booster, and in a hypothetical scenario in which there were no breakthrough infections on or after Day 15.	SARS-CoV-2 infection ≤ 14 days post- booster: Treatment Policy SARS-CoV-2 infection on or after Day 15: Hypothetical ⁸	Imagines a scenario in which breakthrough infections on or after Day 15 did not occur.	The main analysis will be repeated including all
Day-28 Secondary immunological endpoints#	[Geometric mean ratio in [OUTCOME] OR Difference in Mean ACE2 binding inhibition] 28 days after boosting with a single fractional dose compared to a single standard dose of either of the COVID-19 trial vaccines in adults 18 years or older in [Indonesia/Mongolia] who have been primed through previous vaccination with either of the included primary series, irrespective of SARS-CoV-2 infection.	SARS-CoV-2 infection: Treatment Policy	As above	As above	As above	participants through multiple imputation (MICE) of missing outcome and covariate data.
Month-[6/12]^ Secondary immunological endpoints [#]	[Geometric mean ratio in [OUTCOME] OR Difference in Mean ACE2 binding inhibition]# [6/12]^ months after boosting with a single fractional dose (with rescue	SARS-CoV-2 infection: Treatment Policy	, irrespective of SARS-CoV-2 infection ≤ 14 days post-booster or receipt of a 4 th dose	SARS-CoV-2 infection ≤ 14 days post- booster:	As above	

vaccination if required) compared to a single standard dose (without rescue) of either of the COVID-19 trial vaccines in adults 18 years or older in [Indonesia/Mongolia] who have been primed through previous vaccination with either of the included primary series, irrespective of breakthrough infections or receipt of a 4 th dose (self-initiated).	Self-initiated 4 th dose: Treatment Policy	(self-initiated), and in a hypothetical scenario in which there were no breakthrough infections on or after Day 15	Treatment Policy Receipt of 4 th dose (self- initiated): Treatment Policy SARS-CoV-2 infection on or after Day 15: Hypothetical ⁸		
Difference in Mean ACE2 binding inhibition] [6/12] months after boosting with a single fractional dose (with rescue vaccination if required) compared to a single standard dose (without rescue) of either of the COVID-19 trial vaccines in adults 18 years or older in [Indonesia/Mongolia] who have been primed through previous vaccination with either of the included primary series, irrespective of breakthrough infections or receipt of a 4th dose (self-initiated).	SARS-CoV-2 infection: Treatment Policy Self-initiated 4 th dose: Treatment Policy	, irrespective of SARS-CoV-2 infection), and in a hypothetical scenario in which no participants received a self-initiated 4 th dose.	SARS-CoV-2 infection: Treatment Policy Receipt of 4 th dose (self- initiated): Hypothetical ⁸	Imagines a scenario in which no participants received a self-initiated 4 th dose.	
Geometric mean ratio in [OUTCOME] OR Difference in Mean ACE2 binding inhibition] [6/12] months after boosting with a single fractional dose (with rescue vaccination if required) compared to a single standard dose (without rescue) of either of the COVID-19 trial vaccines in adults 18 years or older in [Indonesia/Mongolia] who have been primed through previous vaccination with	SARS-CoV-2 infection: Treatment Policy Self-initiated 4 th dose: Treatment Policy	, irrespective of SARS-CoV-2 infection ≤ 14 days post-booster, and in a hypothetical scenario in which: - there were no breakthrough infections on or after Day 15, AND; -no participants	SARS-CoV-2 infection ≤ 14 days post- booster: Treatment Policy SARS-CoV-2 infection on or after Day 15:	Imagines a scenario in which: -breakthrough infections on or after Day 15 did not occur. AND	
	single standard dose (without rescue) of either of the COVID-19 trial vaccines in adults 18 years or older in [Indonesia/Mongolia] who have been primed through previous vaccination with either of the included primary series, irrespective of breakthrough infections or receipt of a 4th dose (self-initiated). Geometric mean ratio in [OUTCOME] OR Difference in Mean ACE2 binding inhibition] [6/12]^ months after boosting with a single fractional dose (with rescue vaccination if required) compared to a single standard dose (without rescue) of either of the COVID-19 trial vaccines in adults 18 years or older in [Indonesia/Mongolia] who have been primed through previous vaccination with either of the included primary series, irrespective of breakthrough infections or receipt of a 4th dose (self-initiated). Geometric mean ratio in [OUTCOME] OR Difference in Mean ACE2 binding inhibition] [6/12]^ months after boosting with a single fractional dose (with rescue vaccination if required) compared to a single standard dose (without rescue) of either of the COVID-19 trial vaccines in adults 18 years or older in [Indonesia/Mongolia] who have been	single standard dose (without rescue) of either of the COVID-19 trial vaccines in adults 18 years or older in [Indonesia/Mongolia] who have been primed through previous vaccination with either of the included primary series, irrespective of breakthrough infections or receipt of a 4th dose (self-initiated). Geometric mean ratio in [OUTCOME] OR Difference in Mean ACE2 binding inhibition] [6/12]^ months after boosting with a single fractional dose (with rescue vaccination if required) compared to a single standard dose (without rescue) of either of the COVID-19 trial vaccines in adults 18 years or older in [Indonesia/Mongolia] who have been primed through previous vaccination with either of the included primary series, irrespective of breakthrough infections or receipt of a 4th dose (self-initiated). Geometric mean ratio in [OUTCOME] OR Difference in Mean ACE2 binding inhibition] (6/12)^ months after boosting with a single fractional dose (with rescue vaccination if required) compared to a single standard dose (without rescue) of either of the COVID-19 trial vaccines in adults 18 years or older in [Indonesia/Mongolia] who have been primed through previous vaccination with Policy	single standard dose (without rescue) of either of the COVID-19 trial vaccines in adults 18 years or older in [Indonesia/Mongolia] who have been primed through previous vaccination with either of the included primary series, irrespective of breakthrough infections or receipt of a 4th dose (self-initiated). Self-initiated 4th dose: Treatment Policy SARS-CoV-2 infection: Treatment Policy SARS-CoV-2 infection: Treatment Policy SARS-CoV-2 infection: Treatment Policy SARS-CoV-2 infection: Treatment Policy Self-initiated 4th dose: Treatment Policy SARS-CoV-2 infection; and in a hypothetical scenario in which no participants received a self-initiated 4th dose: Treatment Policy SARS-CoV-2 infection; and in a hypothetical scenario in which no participants received a self-initiated 4th dose: Treatment Policy SARS-CoV-2 infection; and in a hypothetical scenario in which no participants received a self-initiated 4th dose: Treatment Policy SARS-CoV-2 infection and happothetical scenario in which no participants received a self-initiated 4th dose. SARS-CoV-2 infection: Treatment Policy SARS-CoV-2 infection: Treatment Policy SARS-CoV-2 infection: Treatment Policy SARS-CoV-2 infection: Treatment Policy SARS-CoV-2 infection and happothetical scenario in which no participants received a self-initiated 4th dose. Treatment Policy SARS-CoV-2 infection and happothetical scenario in which no participants received a self-initiated 4th dose. Treatment Policy SARS-CoV-2 infection and happothetical scenario in which no participants received a self-initiated 4th dose. Treatment Policy SARS-CoV-2 infection on a hypothetical scenario in which no participants received a self-initiated 4th dose. Treatment Policy SARS-CoV-2 infection on a hypothetical scenario in which no participants received a self-initiated 4th dose. Treatment Policy SARS-CoV-2 infection on on a fter Dicky happothetical scenario in which no participants received a self-initiated 4th dose. Treatment Policy	single standard dose (without rescue) of either of the COVID-19 trial vaccines in adults 18 years or older in [Indonesia/Mongolia] who have been primed through previous vaccination with either of the included primary series, irrespective of breakthrough infections or receipt of a 4th dose (self-initiated). Geometric mean ratio in [OUTCOME] OR Difference in Mean ACE2 binding with a single fractional dose (with rescue vaccination if required) compared to a single standard dose (without rescue) of either of the included primary series, irrespective of breakthrough infections or receipt of a 4th dose (self-initiated). SARS-CoV-2 infection: Treatment Policy SARS-CoV-2 infection on or after Dosting in Alphothetical Security of SARS-CoV-2 infection: Treatment Policy SARS-CoV-2 infection on or after Dosting Infection	single standard dose (without rescue) of either of the COVID-19 trial vaccines in adults 18 years or older in [Indonesia/Mongolia] who have been primed through previous vaccination with either of the included primary series, irrespective of breakthrough infections or receipt of a 4th dose (self-initiated). Geometric mean ratio in [OUTCOME] OR Difference in Mean ACE2 binding with a single fractional dose (with rescue) of either of the included primary series, irrespective of breakthrough infections or receipt of a 4th dose: Treatment Policy Geometric mean ratio in [OUTCOME] OR Difference in Mean ACE2 binding with a single fractional dose (with rescue) of either of the included primary series, irrespective of breakthrough infections or receipt of a 4th dose (with rescue) of either of the included primary series, irrespective of breakthrough infections or receipt of a 4th dose (self-initiated). Geometric mean ratio in [OUTCOME] OR Difference in Mean ACE2 binding with a single fractional dose (with rescue) of either of the included primary series, irrespective of breakthrough infections or receipt of a 4th dose (self-initiated). Geometric mean ratio in [OUTCOME] OR Difference in Mean ACE2 binding with a single fractional dose (with rescue) of either of the COVID-19 trial vaccines in adults 18 years or older in [Indonesia/Mongolia] who have been primed through previous vaccination with of the COVID-19 trial vaccines in adults 18 years or older in [Indonesia/Mongolia] who have been primed through previous vaccination with with a single fractional dose (with rescue) of either of the COVID-19 trial vaccines in adults 18 years or older in [Indonesia/Mongolia] who have been primed through previous vaccination with with a single fractional dose (with rescue) of either of the COVID-19 trial vaccines in adults 18 years or older in [Indonesia/Mongolia] who have been primed through previous vaccination with with vaccines in adults 18 years or older in [Indonesia/Mongolia] who have been primed through previous vaccination

Statistical Analysis Plan

Page 38 of 52

irrespective of breakthrough infections or receipt of a 4 th dose (self-initiated).	4 th dose.	Receipt of 4 th dose (self-initiated): Hypothetical ⁸	-no participants received a self- initiated 4 th dose	
--	-----------------------	--	--	--

"This row is generic for all immunological endpoints at the specified timepoint (Table 7). The specified supplementary analyses will be conducted for each endpoint, separately for each trial vaccine. A This row is generic for the Month-6 and Month-12 timepoints. Under the hypothetical strategy, outcome values experienced after the specified intercurrent events will be set to missing and multiple imputation will be used to calculate the estimate including these participants. The parts of the Estimands and intercurrent event strategies that are being modified in the each of supplementary analyses are highlighted by blue text.

6.15.1 Implementation of the Hypothetical Strategy

Under the hypothetical strategy, outcome values experienced after the specified intercurrent events will be set to missing and multiple imputation will be used to calculate the estimate including these participants. For the binary seroresponse outcome, binding antibody levels at Day 28 will be imputed, and then seroresponse will be derived using the imputed value. Multiple imputation will be done using a univariate regression imputation model (logistic regression for binary outcomes and linear regression for continuous outcomes) and 50 imputations. Covariates in the imputation model will be:

- trial vaccine
- study arm (fractional/standard)
- primary series vaccine
- age group
- duration between 1st and 2nd
- duration between 2nd and 3rd doses
- · study day of blood draw
- baseline levels of the outcome variable (for seroresponse, baseline binding antibody as a continuous variable will be included).
- For Month-6 and Month-12 endpoints, levels of the outcome variable at previous blood draws will also be included if the intercurrent
 event occurred after these visits.

6.15.2 Strategy for multiple imputation

Multiple imputation will be done using a multivariate imputation model (MICE) and 50 imputations. Covariates in the imputation model will be the same as those specified for imputation under the hypothetical strategy (Section 6.15.1 Implementation of the Hypothetical Strategy). For the binary seroresponse outcome, binding antibody levels will be imputed (rather than the relative increase from baseline or binary seroresponse), and then seroresponse will be derived using the imputed value/s.

6.16 SUBGROUP ANALYSES AND TESTS FOR INTERACTION

Analyses will be conducted separately for each study (the Indonesia Trial, BCOV22 [concatenated with BCOV21], and the Mongolia Trial). Analyses will also be conducted on concatenated data of the Indonesia Trial and BCOV21/22.

Analyses for all endpoints will be conducted separately for the different booster vaccines, amongst all strata combined. Subgroup analyses by the primary series strata will also be conducted for the primary endpoints, and all binding antibody, ACE2 binding inhibition, safety and breakthrough infection secondary endpoints. Tests of interaction will be done for the primary immunogenicity endpoint and secondary endpoint (i) (see 5.2 Secondary) by fitting a model with an interaction parameter between study arm and primary series strata.

6.17 ANALYSIS OF SAFETY ENDPOINTS

Analyses for all safety endpoints (5.3 Safety endpoints) will be amongst all randomised participants according to the trial vaccine received (the "Safety Population"). Recurrent events in the same individual will be counted as a single event (using information from the most severe occurrence); all recurrences will be included in the line list of all adverse events. Population measures for all safety endpoints (5.3 Safety endpoints) will be reported separately for standard and fractional dose groups, by trial vaccine. Analyses of all safety endpoints will be descriptive only. Missing data on severity, onset, SOC, causality, SAE outcome, and SAE expectedness will be described by study group.

In addition, a list of all adverse events will be provided by third dose allocation, trial vaccine, and primary series vaccine, including the following parameters:

- the patient identifier
- age
- sex
- weight
- height
- adverse event (reported term, lower-level term, and SOC)
- day of onset (from Day 0)
- days since receipt of 4th COVID-19 vaccine dose (self-initiated or as rescue) (if applicable)
- duration (in days)
- severity grade
- seriousness (serious/non-serious)
- special interest (yes/no)
- expectedness (yes/no)
- action taken
- outcome (Resolved, Resolved with sequelae, Ongoing, Fatal and Unknown)
- causality assessment/relatedness (noting 'adverse reactions' and 'serious adverse reactions')
- concomitant medication at baseline
- concomitant medication during study (prior to event)
- concomitant medication in response to event
- comorbidities at baseline
- brief narrative (SAEs only)

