5.3 SAFETY ENDPOINTS

Table 8. Safety endpoints

Safety Endpoint	Outcome	Timepoint	Population measure	Comparison	Measure of association
i.	Any# AE to Day 28 (inclusive)*	28 days post- booster	Frequency [N (%)]	Fractional vs. Standard	Descriptive only
ii.	Any# AE to Day 28 (inclusive)* ^ by severity	28 days post- booster	Frequency [N (%)]	Fractional vs. Standard	Descriptive only
iii.	Any# AE to Day 28 (inclusive)* ^ by causality assessment	28 days post- booster	Frequency [N (%)]	Fractional vs. Standard	Descriptive only
iv.	Any AE to Day 28 (inclusive)* by SOC and severity^	28 days post- booster	Frequency [N (%)]	Fractional vs. Standard	Descriptive only
v.	Duration# of AE to Day 28 (inclusive)* by SOC^	28 days post- booster	Median days {25 th – 75 th percentile}, min - max	Fractional vs. Standard	Descriptive only
vi.	Day of AE onset (days post-booster) to Day 28 (inclusive)* by SOC^	28 days post- booster	N by Day	Fractional vs. Standard	Descriptive only
vii.	AE to Day 28 (inclusive)* by Outcome**^	28 days post- booster	Frequency [N (%)]	Fractional vs. Standard	Descriptive only
viii.	Medically attended unsolicited AE to Month-3 visit (inclusive)	90 days post- booster	Frequency [N (%)]	Fractional vs. Standard	Descriptive only
ix.	SAE to study-end by SOC and expectedness ^a	Month-12 visit	Frequency [N (%)]	Fractional vs. Standard	Descriptive only
x.	SAE to study-end by Outcome**^	Month-12 visit	Frequency [N (%)]	Fractional vs. Standard	Descriptive only

[&]quot;The Safety analysis will only include unsolicited adverse events; solicited adverse events are considered in the Reactogenicity analysis. "Adverse events within 28 days inclusive will be considered, rather than all adverse events prior to the Day-28 visit, which can occur between 28- and 35-days post-booster. "Outcome categories are Resolved, Resolved with sequelae, Ongoing, Fatal and Unknown; denominator is the total number of SAEs rather than the number of participants. 'Recurrent events in the same individual will be counted as a single event (using information from the most severe occurrence); all recurrences will be included in the line list of all adverse events. "Event duration of 'Ongoing' adverse events will be the number of days between onset and the last visit.

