GMR (95% CI)	Ref	x.xx (x.xx-x.xx)	Ref	x.xx (x.xx-x.xx)				
Neutralising antibody (Omicron), NT ₅₀								
GMT (95% CI)	xxx (xxx-xxx; n=xx)	xxx (xxx-xxx; n=xx)	xxx (xxx-xxx; n=xx)	xxx (xxx-xxx; n=xx)				
GMR (95% CI)	Ref	x.xx (x.xx-x.xx)	Ref	x.xx (x.xx-x.xx)				
IFNγ, IU/ml								
GMT (95% CI)	xxx (xxx-xxx; n=xx)	xxx (xxx-xxx; n=xx)	xxx (xxx-xxx; n=xx)	xxx (xxx-xxx; n=xx)				
GMR (95% CI)	Ref	x.xx (x.xx-x.xx)	Ref	x.xx (x.xx-x.xx)				
IFNγ-producing cells, cells/million PBMCs								
GM (95% CI)	xxx (xxx-xxx; n=xx)	νοιχ (xxx-xxx; n=να)	xxx (xxx-xxx; n=xx)	xxx (xxx-xxx; n=xx)				
GMR (95% CI)	Ref	x.xx (x.xx-x.xx)	Ref	x.xx (x.xx-x.xx)				

[figure not shown]
GMT: Geometric mean titre; GMR: geometric mean ratio; GM: geometric mean; MD: difference in means; Ref: Reference group. *Inhibition of binding between the SARS-CoV-2 receptor binding domain and the host-cell ACE2 receptor by neutralising antibody.

Dummy Table S 3. Frequency and outcomes of unsolicited adverse events and serious adverse events

[figure not shown]
	Boost with Comirnaty®			
	Total	Standard	Fractional	1
	(N = n)	(N = n)	(N = n)	Additional columns will be ad
Any AE to Day 28 (inclusive) *	N (%)	N (%)	N (%)	Spikevax® and Vaxzevria® gr
Any Grade 3 - 5 AE to Day 28 (inclusive)*^	N (%)	N (%)	N (%)	Indonesia
AE Outcome#				
Resolved	N (%)	N (%)	N (%)	
Resolved with sequelae	N (%)	N (%)	N (%)	
Ongoing	N (%)	N (%)	N (%)	
Fatal	N (%)	N (%)	N (%)	
Unknown	N (%)	N (%)	N (%)	
Medically attended AE to Month- 3 visit (inclusive)	N (%)	N (%)	N (%)	
Any SAE to study-end ^a				
SOC A	N (%)	N (%)	N (%)	
SOC B	N (%)	N (%)	N (%)	
SOC C	N (%)	N (%)	N (%)	
for all SOCs	N (%)	N (%)	N (%)	
SAE Outcome#				
Resolved	N (%)	N (%)	N (%)	
Resolved with sequelae	N (%)	N (%)	N (%)	
Ongoing	N (%)	N (%)	N (%)	
Fatal	N (%)	N (%)	N (%)	
Unknown	N (%)	N (%)	N (%)	

^{*}Unsolicited Adverse events within 28 days inclusive will be considered, rather than all adverse events prior to the Day-28 visit, which can occur between 28- and 35-days post-booster. 'Recurrent events in the same individual will be

counted as a single event (using information from the most severe occurrence); all recurrences will be included in the line list of all adverse events. "Denominator is the total number of AEs/SAEs rather than the number of participants.

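### The single most-severe-occurrence rule also governs causality and day of onset, so recurrent events can understate adverse reactions and delay onset; the AE-outcome denominator is also wrong

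*SAP*

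**What the plan says.** SAP 6.17, in a paragraph on all safety endpoints, states: "Recurrent events in the same individual will be counted as a single event (using information from the most severe occurrence". It adds that "all recurrences will be included in the line list of all adverse events"; that list carries each event's severity, causality, onset, duration and outcome.

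SAP 5.3, Table 8, repeats the rule as its '^' footnote. The marker is on severity (rows ii and iv), causality (row iii, "Any# AE to Day 28 (inclusive)* ^ by causality assessment"), duration (row v), onset (row vi, "Day of AE onset (days post-booster) to Day 28 (inclusive)* by SOC"), AE outcome (row vii) and SAE outcome (row x). No section gives a different rule for any of these attributes, defines recurrent, or says what to do when occurrences have the same grade.

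The '**' footnote of Table 8, attached to rows vii and x, says the "denominator is the total number of SAEs rather than the number of participants". The footnote to Dummy Table S 3 (SAP 7.1.2) says: "Denominator is the total number of AEs/SAEs rather than the number of participants".

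**The concern.** Choosing the most severe occurrence is the usual rule for a severity table. For causality the question is whether the participant had any event judged related to the vaccine. For onset it is when the event first appeared. An occurrence chosen on grade need not answer either question.

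SAP 4.2 (Table 4) lists adverse reactions to 28 days as an outcome, defined by a causality grade of possible or stronger. Row iii is the Table 8 endpoint that summarises causality. If the rule is followed as written, row iii can show fewer participants with an adverse reaction than the data contain. The shortfall could differ between dose arms if one arm has more repeated events.

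The denominator is a separate fault. Row vii describes the outcomes of all unsolicited AEs to Day 28, but its footnote divides them by a count of SAEs.

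**Working it through.** The documents attach no event count or rate to this rule, so there is no plan figure to reproduce. All rates below are assumptions.

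**1. The rule applied to one invented participant.** The same event occurs twice and resolves each time: Day 2, grade 1, Probable; then Day 20, grade 2, Unrelated. The rule tabulates one event: Day 20, grade 2, Unrelated. The severity row is right. Row iii shows no adverse reaction, and row vi shows Day 20 instead of Day 2.

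**2. Direction.** If the most severe occurrence is related, the participant has a related event; the converse does not hold. So the number of participants with a related AE can fall but never rise. Likewise the onset of the selected occurrence can equal the first onset or follow it, but never precede it.

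**3. Size of the causality loss, recurrent = repeats of the same event.** Take two occurrences. Let r be the chance that an occurrence is related, c the within-person concordance of relatedness, and let severity be independent of relatedness (ties broken at random). Then

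P(tabulated as unrelated | at least one related) = (1−c)r(1−r) / [r² + c·r(1−r) + 2(1−c)r(1−r)].

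| r | c = 0 | c = 0.5 | c = 0.9 | c = 1 |
|---|---|---|---|---|
| 0.2 | 0.160/0.360 = 44% | 0.080/0.280 = 29% | 0.016/0.216 = 7% | 0 |
| 0.5 | 0.250/0.750 = 33% | 0.125/0.625 = 20% | 0.025/0.525 = 5% | 0 |
| 0.8 | 0.160/0.960 = 17% | 0.080/0.880 = 9% | 0.016/0.816 = 2% | 0 |

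These shares apply only to participants with a recurrence. If 5–10% of participants with a related AE have one (assumed), then at r = 0.2 the overall loss is 0.05–0.10 × 7.4% = 0.4–0.7% at c = 0.9, and 0.05–0.10 × 28.6% = 1.4–2.9% at c = 0.5.

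**4. Size of the causality loss, recurrent = any AE in the person.** Let each person have a Poisson number of AEs with mean m, each related with probability r, independently of each other and of severity. The true share with a related AE is 1 − exp(−mr). The rule reports r(1 − exp(−m)).

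| m | relative loss, r = 0.2 | relative loss, r = 0.4 |
|---|---|---|
| 0.2 | 7.5% | 5.7% |
| 0.4 | 14.2% | 10.8% |
| 0.7 | 22.9% | 17.5% |
| 1.0 | 30.3% | 23.3% |

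For example, with m = 0.4 and r = 0.4: 1 − exp(−0.16) = 14.8% against 0.4 × (1 − exp(−0.4)) = 13.2%, or about 59 against 53 of the 400 participants per arm. Simulation gave the same range. When half the events shared a person-level causality status, the simulated loss fell to about 4–24%, with the same sign.

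**5. Onset and ties.** With two occurrences and grade probabilities p, the chance of equal grades is Σp², and the chance that the second is strictly more severe is (1 − Σp²)/2.

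| Assumed mix, grades 1/2/3 | tie | second more severe |
|---|---|---|
| 70/25/5 | 0.490 + 0.0625 + 0.0025 = 56% | 22% |
| 50/40/10 | 0.250 + 0.160 + 0.010 = 42% | 29% |
| 90/9/1 | 0.810 + 0.0081 + 0.0001 = 82% | 9% |

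Under these mixes the SAP has no answer for 42–82% of two-occurrence cases.

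**6. Denominator.** Row vii counts AEs, its '**' footnote divides by SAEs, and Dummy Table S 3 divides by AEs or SAEs as the row requires. Under the footnote, any outcome category with more AEs than there are SAEs exceeds 100%. The SAP also does not say whether the denominator counts collapsed events or all occurrences.

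**The case against.** In ordinary use, recurrent means a repeat of the same event. Protocol 8.3 fits this, since it has intermittent AEs recorded episode by episode. On that reading distinct AEs in one person are never collapsed into each other, and repeats of one event will often receive the same causality grade, in which case nothing is lost. This argument stands. A reader might infer from step 4 that 6–30% of participants with an adverse reaction will be missed, or that an unrelated event can displace a related event of a different kind. Both need the any-AE reading, which the SAP does not state and which is the less natural one.

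A reader might also infer that adverse reactions vanish from the report. They do not: the line list (Table S5) keeps every occurrence with its causality. It is also the only planned output that shows relatedness, since Dummy Table S 3 has no causality rows. But row iii is still a listed endpoint, and it should be computed correctly when it is reported.

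A third inference is that duration ("Duration# of AE to Day 28 (inclusive)* by SOC") and outcome are also read from the wrong episode. That is a preference. Reporting one coherent episode is defensible, and counting every occurrence would let one participant with many episodes dominate an SOC's median duration.

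The scope is narrow. Table 8 covers unsolicited events only, solicited reactions are analysed separately, and every safety endpoint is descriptive. No test, margin or non-inferiority conclusion is affected.

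The denominator footnote may be a drafting slip, with Dummy Table S 3 showing the intent. It is still a contradiction between two current parts of the SAP.

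**Conclusion.** The point holds in a limited form. The SAP states one rule, selection on severity, and applies it to causality and onset, where it can only understate related AEs and only delay onset. For causality this needs recurrences that differ in relatedness, with the more severe one unrelated or less related. For onset it needs a later occurrence that is the more severe.

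The size cannot be established from the documents. Under the same-event reading and the assumptions in step 3 (5–10% of participants with a related AE having a recurrence, r = 0.2), the causality loss is roughly 0.4–3% of those participants, and zero if causality always agrees. Only the any-AE reading gives the larger figures of step 4. The undefined term and the missing tie rule also mean that two analysts could produce different causality summaries from the same data. Double programming (SAP 6.1.4) is specified for the primary immunological endpoint only and would not expose this.

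The row vii denominator is wrong as written, whatever the AE rates.

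**What to change.** In SAP 6.17 and the Table 8 footnotes:

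- Keep the most-severe rule for the severity rows (ii, iv).
- For causality (row iii), use the strongest relatedness among the recurrences.
- For onset (row vi), use the earliest onset within the SOC.
- Define recurrent (for example, same reported or coded term) and add a rule for occurrences of equal grade.
- Change the '**' denominator to all AEs for row vii and all SAEs for row x, as in Dummy Table S 3. State that numerator and denominator are counted on the same basis, either both collapsed or both all occurrences.

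Duration and outcome can stay as they are, taken from one episode.

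The cost is a few sentences and a few lines of code. No new data are needed, because episodes are already recorded separately. The downside is that the related-AE percentage may be slightly higher, and the severity and causality rows may draw on different occurrences for the same person, which a table note should say.
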